General Study Design: The proposed study is a prospective, randomized, clinical trial with attention control under the direction of the dual PIs, a behavioral scientist and a virologist. The study team is also made up of investigators from infectious diseases, mind-body medicine, geriatrics, and biostatistics. Subjects will be randomized to participation in an 8-week group MBSR course as the study intervention or to the Health Enhancement Program (HEP) as the active control arm. The study population will consist of 120 individuals, 50 years old or older, long-term (5 years on ART or longer) HIV-infected adults with well-controlled plasma viremia. Randomization will be stratified to achieve balanced distribution between the groups based on gender and study site. The experimental group will participate in the 8-week MBSR course followed by six, once-per-month booster sessions, and the control group will participate in HEP, a validated group attention control condition for MBSR maintaining subjects inert to mindfulness, with additional monthly educational meetings for

six months. Both groups will be evaluated using two sets of measures: biological markers associated with chronic inflammation (IL-6, CRP, sCD14, d-dimer) and measures of psychosocial stress (anxiety, depression, fatigue, and mindfulness). Subjects will be assessed at three time points: baseline, 8 weeks (immediately after completion of MBSR intervention), and 6-months post MBSR course (immediately after completion of booster sessions). We will use mixed linear and structural equation model to test study hypotheses.

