Aim 1: To assess the effect of MBSR on biomarkers of chronic inflammation in HIV-infected adults with well-controlled plasma viremia. The primary outcome for the analyses of treatment effectiveness will be IL-6 levels. We will use mixed linear models to assess the effect of the intervention on markers of inflammation. The model will include fixed effect terms for treatment group, time, and time-treatment interactions. In secondary analyses, we will similarly assess the effect of the intervention on secondary markers of inflammation (CRP, sCD14, d-dimer) using appropriate adjustments for multiple comparisons. If there are imbalances in patients’ characteristics across groups, statistical adjustment including these factors as covariates will be performed. All analysis will use an intent-to-treat principle. **Power Calculation:** Sample size calculations were based on the following assumptions: 1) mean baseline IL-6 of 2.0 pg/ml (SD:0.5)^{17,98}; 2) stable IL-6 levels in the control arm; 3) clinical significant effect of MBSR will be a net reduction of IL-6 of >0.5 pg/ml.^{98,99} Under these assumptions, a sample size of 100 patients (50 per group) will provide a power >80% using 2-sided test and a 0.05 significance level. One hundred and twenty study participants will be enrolled. Dropout rates reported in the literature for MBSR studies range significantly (range 0 to 48%, mean 10%). In order to lean on a conservative side a higher dropout rate of 15% is estimated for this study. With a 120 enrolled, a 15% dropout rate provides 102 completed participants. It is quite feasible to recruit 120 patients from this estimated eligible sample of 1,800 subjects at the three recruitment sites (requiring participation of ~7% of the eligible sample).

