Aim 2: To explore whether changes in markers of psychosocial stress mediate the impact of MBSR on chronic inflammation. We will compare depression, anxiety, fatigue, and mindfulness scores among subjects in the active vs. control arm using a t-test or Wilcoxon test, as appropriate. The association between depression, anxiety, fatigue, and mindfulness scores with IL-6 (and other inflammatory markers) will be tested using the Pearson correlation coefficient. SEM analyses (using Mplus) will be based on the preliminary model depicted in Figure 1. We hypothesize that MBSR will impact inflammatory markers indirectly via effect on markers of psychosocial stress and mindfulness. Latent variables will be measured using a combination of factor scores (i.e., parceling) and items. Psychosocial stress will be measured with four factors (e.g., depression, anxiety, fatigue, mindfulness) allowing for the testing of specific pathways. This model will also include control variables. We will estimate parameters by using Weighted Least Squares Mean-Variance adjusted (WLSMV) estimator. The WLSMV method provides a robust estimation when sample size is moderate. Model fit will be evaluated based on various indices of exact and close fit: χ^2 (>0.05), the comparative fit index (CFI>0.90), the Tucker-Lewis fit index (TLI>0.90), the root mean squared error of approximation (RMSEA<0.05), and the weighted root mean square residual when using WLSMV (WRMR<0.90). To ensure consistent parameter estimates, we will estimate models including a latent class variable identifying the patterns of missingness. These analyses will be conducted using a latent class pattern mixture model. **Sample Size Calculations** were performed using the method presented by MacCallum et al.¹⁰⁰ Effect size in this approach is defined in terms of a null hypothesis and alternative hypothesis value of the root-mean-square error of approximation (RMSEA) index, which we hypothesized would be 0.05 (adequate fit) and 0.03 (good exact fit), respectively. We estimated that we would have, at minimum, 80 degrees of freedom, having a sample size of 120 subjects, and an error rate (alpha) of 0.05. Under these specified assumptions we will have >80% power.

Data Safety Monitoring Board (DSMB) Dr. [name] and Dr. [name] will serve on the DSMB for the study. The DSMB will meet twice yearly and [name] and [name] will attend the DSMB meetings.

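### Aim 2 is about changes, but its arm comparison has no visit or baseline term and its Pearson test no visit, change or arm term; both can be improved cheaply

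*Combined protocol and SAP*

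**What the plan says.** All of this is in the combined protocol and SAP, section C (Approach).

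- **Aim 2, purpose:** "To explore whether changes in markers of psychosocial stress mediate the impact of MBSR on chronic inflammation".
- **Aim 2, arm comparison:** "We will compare depression, anxiety, fatigue, and mindfulness scores among subjects in the active vs. control arm using a t-test or Wilcoxon test".
- **Aim 2, association:** "The association between depression, anxiety, fatigue, and mindfulness scores with IL-6 (and other inflammatory markers) will be tested using the Pearson correlation coefficient".
- **Measures of Psychosocial Stress and Mindfulness:** the scales are completed at baseline, after the 8-week course and after the booster period, so a score can come from any of three visits.

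Four other statements come close to filling the gap:

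- **General Study Design:** "We will use mixed linear and structural equation model to test study hypotheses". Aim 2 then names different tests for the scales.
- **Aim 1:** "We will use mixed linear models to assess the effect of the intervention on markers of inflammation". The group, time and interaction terms are stated for the inflammatory markers. If the arms are imbalanced, "statistical adjustment including these factors as covariates will be performed"; this also sits under Aim 1 and is conditional.
- **Attention control arm, potential challenges:** analyses of within-subject differences are promised in general but tied to no test.
- **Aim 2, structural equation model (SEM):** it will include control variables, which are not listed. This is the mediation test.

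On allocation, General Study Design says: "Randomization will be stratified to achieve balanced distribution between the groups based on gender and study site".

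**The concern.** The aim concerns change, while both supporting tests are written on scores with no visit named. The two tests have different gaps.

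- **Arm comparison.** It contrasts the arms, as it should, but leaves out the baseline score that every subject will have given. The cost is precision.
- **Pearson correlation.** It has no arm term, and both natural readings miss the question. Taken at a single visit, it picks up stable differences between people: those with more symptoms may simply have higher IL-6 throughout. That is a real association, but not one of changes. Taken on changes pooled over the arms, it can be produced by MBSR moving the scale and the marker by unrelated routes.

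Four scales and four markers give 16 correlations at each visit. A significant one would easily be read as support for the proposed mechanism.

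**Working it through.** The plan gives no power or sample size for either test, so it has no figure of its own to reproduce here.

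**Inputs from Aim 1, Power Calculation**
- Completers: 120 × (1 − 0.15) = 102, taken as 51 per arm.
- Two-sided 0.05, and 80% power as the benchmark.
- IL-6: "mean baseline IL-6 of 2.0 pg/ml (SD:0.5", and a net reduction of 0.5 pg/ml as the effect of interest. 0.5 / 0.5 = 1 SD.

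**Assumed, not in the documents:** the baseline/follow-up correlation r (in the simulations, the share of variance that is stable between visits), the correlation between the stable parts of scale and marker, and the MBSR effect on a scale.

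**Arm comparison: detectable difference in SD units**

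For follow-up scores alone, the t-test with 51 per arm gives 0.560. The normal approximation, (1.960 + 0.842) × √(2/51), gives 0.555. Change scores multiply 0.560 by √(2(1 − r)); baseline adjustment multiplies it by √(1 − r²).

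| r | Follow-up only | Change score | Baseline-adjusted |
|---|---|---|---|
| 0.3 | 0.560 | 0.663 | 0.534 |
| 0.5 | 0.560 | 0.560 | 0.485 |
| 0.7 | 0.560 | 0.434 | 0.400 |

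Baseline adjustment is the best of the three at each value.

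**Association**

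Simulation: 102 subjects, 10,000 runs per setting, each measure = stable part + independent visit noise, changes unrelated apart from arm effects.

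1. *Single-visit scores, no arm effects.* The expected correlation is stable share × stable correlation, for example 0.6 × 0.3 = 0.18. At share 0.6 the test is significant in 9%, 44% and 87% of trials at stable correlation 0.1, 0.3 and 0.5. Over shares 0.5 to 0.7 the ranges are 8–11%, 32–57% and 73–96%.
2. *Separate arm effects, IL-6 1 SD and score 0.5 SD, stable correlation 0.* With equal arms and share 0.6, the pooled covariance of changes is 0.5 × 1 / 4 = 0.125. The variances are 2(1 − 0.6) + 0.5²/4 = 0.8625 for the score and 0.8 + 1²/4 = 1.05 for IL-6. So r = 0.125 / √(0.8625 × 1.05) = 0.13, with no link within either arm. The pooled-change test is significant in 26–27% of trials, and in 19–40% over shares 0.5 to 0.7. On single-visit scores it is 19–20%. Separate runs put the low end at about 18%.
3. *The same with a 0.2 SD score effect.* Pooled change: 7–11%.
4. *Change on change, adjusted for arm.* 4.5–5.7% in every setting above.

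**Limits of the arm-adjusted test**

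- *Correlated visit noise.* The 5% rests on independent noise. If noise in scale and marker correlates 0.1, 0.2 or 0.3 at a visit (share 0.6, no arm effect), the arm-adjusted test is significant in 17%, 52% or 87% of trials.
- *Power under true mediation.* With full mediation, slope 0.2 and share 0.6, pooled change is significant in 54% (score effect 0.5 SD) or 62% (1 SD), against 51% adjusted for arm.

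**The case against.** The case on the other side has several parts.

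- **The arm comparison already has an arm term and is sound.** This stands. A reader might infer that both tests ignore arm, or that the t-test is biased. The text does not support either: the t-test contrasts the randomised arms and, on follow-up scores, is unbiased. Only the Pearson test lacks an arm term.
- **The 9%, 44% and 87% look like false-positive rates but are not.** This stands. A real between-person correlation is being detected. The figures show that a significant result need not concern change.
- **Arm-adjusted change does not isolate mediation.** This stands. The plan itself warns, in its discussion of the control arm, that weather and seasonal illness may affect outcomes. A cold could move fatigue and IL-6 together. Running the arms concurrently protects the arm contrast, not this association.
- **The change is not free.** This stands. Change scores are noisier than levels when the baseline/follow-up correlation is below 0.5, some power is lost if mediation is real, and transformation does not remove ties if scores cluster near the floor.
- **The plan covers this elsewhere.** This stands only in part. The general statements on mixed models and within-subject differences do not exclude a better analysis, but neither attaches a visit, baseline or arm term to these tests. The SEM may contain such terms; its figure is not available to check, and the two quoted tests would be unchanged.
- **The aim is exploratory.** This stands and limits the weight of the point.

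**Conclusion.** The point holds as a minor improvement to two supporting tests.

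- **Arm comparison:** valid but less precise than it could be. The detectable difference falls from 0.56 SD to between 0.53 and 0.40 SD for assumed correlations of 0.3 to 0.7.
- **Pearson test:** it does not address linked changes on either reading. Separate arm effects make it significant in about 18–40% of trials, against about 5% with arm adjustment. This uses the plan's 1 SD IL-6 effect, an assumed 0.5 SD score effect and stable shares of 0.5 to 0.7. With a 0.2 SD score effect the pooled-change figure is only 7–11%.

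A reader might infer that the mediation conclusion or the trial's main result is at risk. The documents do not support that. The SEM is the mediation test, Aim 2 is exploratory, and the IL-6 analysis under Aim 1 does not depend on either test. No view is taken here on the SEM's own power or specification.

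**What to change.** In the Aim 2 text:

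1. **Arm comparison.** Analyse each scale with a mixed model of the 8-week and 6-month scores, with arm, visit, arm-by-visit, baseline score and the stratification factors (gender and site). Keep a rank-based test as a sensitivity analysis for skewed or tied scores.
2. **Association.** Name the visit. Report the association of change from baseline in each score with change from baseline in each marker at that visit, adjusted for arm, with confidence intervals. Describe it as descriptive support for the SEM and not as a test of mediation, because shared visit-level influences can also correlate changes. Do not adjust for both baselines as well: they are noisy, and in the simulations this let stable between-person correlation back in (7–8% significant at stable correlation 0.3, 10–16% at 0.5).
3. **SEM.** Leave it as the mediation test.

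The cost is a few sentences of plan text and a few degrees of freedom. The association also carries noisier change scores if the baseline/follow-up correlation is below 0.5, and a small loss of power if mediation is real. No new data, visits or subjects are needed, and Aim 1 is unchanged.

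### Aim 2 asks whether stress and mindfulness mediate the MBSR effect, but its only power figure is for model fit, and no estimate or interval for the indirect effect is planned

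*Combined protocol and SAP*

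**What the plan says.** All of this is in the combined protocol and SAP, section C (Approach), Data Management and Statistical Analysis, under Aim 2.

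- **Question:** "To explore whether changes in markers of psychosocial stress mediate the impact of MBSR on chronic inflammation".
- **Hypothesis:** "We hypothesize that MBSR will impact inflammatory markers indirectly via effect on markers of psychosocial stress and mindfulness".
- **Analyses of effects:** arm comparisons of depression, anxiety, fatigue and mindfulness by t-test or Wilcoxon test; Pearson correlations of those scores with IL-6 and the other markers; and a structural equation model that is said to permit tests of particular pathways. No test, interval or threshold is given for any pathway.
- **Numeric criteria for the model:** all concern global fit: "Model fit will be evaluated based on various indices of exact and close fit". They include "χ^2 (>0.05), the comparative fit index (CFI>0.90" and "the root mean squared error of approximation (RMSEA<0.05", with further cut-offs for TLI and WRMR.
- **Sample size:** "Effect size in this approach is defined in terms of a null hypothesis and alternative hypothesis value of the root-mean-square error of approximation", with the two values "which we hypothesized would be 0.05 (adequate fit) and 0.03 (good exact fit), respectively". The inputs are at least 80 degrees of freedom, 120 subjects and alpha 0.05. The stated result is power above 80%.

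Under Aim 1, the plan expects 102 completers out of 120 enrolled.

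**The concern.** A mediation hypothesis is a statement about an indirect effect: the arm-to-mediator path multiplied by the mediator-to-marker path. Global fit indices assess the restrictions a model imposes. They do not assess the size of paths that are freely estimated. A trial in which MBSR changes nothing is a special case of the same model, with the arm paths at zero, and it fits as well as one in which MBSR works.

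A power figure for RMSEA therefore answers a different question from the one Aim 2 asks. A reader who sees more than 80% power under a mediation aim will take it as the chance of detecting mediation.

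The other planned analyses do not fill the gap. The arm comparison bears on the first link only. The correlation is not stated to be adjusted for arm, so it is not the second link as a mediation model defines it. The pathway tests come with no rule for combining paths into an indirect effect.

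**Working it through.** **1. The plan's own power figure.** The inputs from Aim 2 are df = 80, N = 120, alpha = 0.05, null RMSEA 0.05 and alternative RMSEA 0.03. Under the RMSEA approach, the test statistic is noncentral chi-square with noncentrality (N − 1) × df × RMSEA².

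- Null: 119 × 80 × 0.0025 = 23.8.
- Alternative: 119 × 80 × 0.0009 = 8.568.
- The test rejects the null for small values. The 5th percentile under the null is 78.94.
- Power = P(statistic < 78.94 under the alternative) = 0.253.

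The stated figure does not reproduce. Variants on the same inputs:

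| Variant | Power |
|---|---|
| As stated, N − 1 | 25.3% |
| N in place of N − 1 | 25.6% (25.55%) |
| Hypotheses reversed (0.03 null, 0.05 alternative) | 27.8% |
| Alpha 0.10 | 38.6% |
| Alternative RMSEA 0 | 48.8% |
| 0.05 against 0.08 | 67.1% |
| 0.05 against 0.08, alpha 0.10, N in place of N − 1 | 79.0% |
| As stated, N = 102 | 21.2% |

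None reaches 80%. With the stated RMSEA values and alpha, 80% needs N of about 368 at df 80, or df of about 485 at N = 120. The plan gives 80 as a minimum for the degrees of freedom, so a larger model would raise the power, but it would have to be about six times that minimum.

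**2. What the fit cut-offs say about a treatment with no effect.** Set all MBSR paths to zero and let the rest of the model be correct. The fit statistic is then central chi-square with 80 df.

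- Chi-square p > 0.05 means a statistic below 101.88.
- Estimated RMSEA < 0.05 means a statistic below 80 + 80 × (N − 1) × 0.0025. This is 103.8 at N = 120 and 100.2 at N = 102.

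| True RMSEA of the rest of the model | Passes both, N = 120 | Passes both, N = 102 |
|---|---|---|
| 0 | 95.0% | 93.7% |
| 0.02 | 90.8% | 89.7% |
| 0.03 | 83.2% | 82.9% |

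A finite-sample simulation of an assumed mediation model with zero MBSR paths (normal-theory maximum likelihood, df 105, about 500 runs at each N) gave about 86% at both N = 102 and N = 120, because the chi-square statistic runs high in small samples. WLSMV, the planned estimator, was not simulated.

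**3. What power for the indirect effect might be.** The documents give no path sizes, so those below are assumptions. Take one observed mediator at N = 102, with d the standardized arm effect on the mediator and b the mediator-to-IL-6 path, treated as a partial correlation. Call mediation detected when both paths are significant at the two-sided 5% level:

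power ≈ Φ(d√N/2 − 1.96) × Φ(atanh(b)√(N − 4) − 1.96).

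For d = 0.5 and b = 0.3: Φ(2.525 − 1.96) × Φ(3.064 − 1.96) = 0.714 × 0.865 = 0.618.

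| d | b | Formula | Simulation (8,000 runs) |
|---|---|---|---|
| 0.3 | 0.3 | 28.4% | 27.9% |
| 0.5 | 0.3 | 61.8% | 60.6% |
| 0.5 | 0.4 | 70.5% | 69.5% |
| 0.8 | 0.3 | 84.9% | 84.9% |

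**The case against.** The plan can be defended on several grounds.

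- **Fit is not offered as proof of mediation.** A reader might infer that good fit would be taken as support for the hypothesis. The documents do not say so. They say only that fit will be evaluated, which is ordinary practice for a structural equation model. This stands.
- **Effects are analysed.** It would be wrong to say that Aim 2 looks at nothing but fit. If MBSR did nothing, the arm comparisons and arm paths would usually show it. This also stands. Moreover, the power figures above rest on two path tests taken together, so the planned pathway tests are not far from a mediation test. What is missing is the rule for combining them and an interval for the product.
- **The 95% pass rate is close to a truism.** Any correct model passes a 5% exact-fit test 95% of the time. The figure is nominal and covers two of the five indices. Pass rates for CFI, TLI and WRMR depend on loadings the documents do not give. It supports the narrow statement that fit cannot stand in for a test of mediation, and no more.
- **The aim is exploratory, and the model figure is not in the supplied text.** The exploratory wording lowers the weight of the point, and Aim 1 is untouched. Whether the figure draws a direct path cannot be judged. However, the Innovation section presents the mediation question as a first, and Aim 2 states both a hypothesis and a power. Neither the exploratory wording nor a path diagram would correct that power figure.

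**Conclusion.** The point holds in a limited form. The Aim 2 power statement concerns model fit rather than mediation, and as a fit calculation it gives about 25% instead of more than 80%. It therefore supports neither purpose. The planned analyses yield no estimate or interval for the indirect effect, and the fit cut-offs cannot provide one.

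The 25% rests only on the plan's inputs and the standard noncentral chi-square calculation. The 94–95% pass rate assumes a correct model and a chi-square at its reference distribution; about 83–91% is more realistic under mild misspecification or small-sample inflation. The 28–85% range for mediation rests on assumed path sizes and a single observed mediator, not on the planned latent factors. Because the aim is exploratory, this is a change that should be made; it is not a threat to the trial's primary result.

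**What to change.** In Aim 2:

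1. Make the indirect effect on IL-6 the estimand: the arm-to-mediator path times the mediator-to-IL-6 path, with the direct arm-to-IL-6 path left free. State which visits supply the mediator and the outcome.
2. Report it with a 95% interval suited to a product of paths, such as a percentile bootstrap, provided this is compatible with the chosen estimator and missing-data method. Base any statement about mediation on that interval.
3. Either label the four mediators (and any analyses of the other markers) as exploratory, or adjust for multiplicity.
4. Keep the fit indices as model checks only.
5. Replace the RMSEA power sentence with the indirect effect detectable at 102 completers, with path sizes stated as assumptions.

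The cost is SAP wording, some programming, and a check that the interval method works with WLSMV and the planned handling of missing data. No extra patients, visits or assays are needed. The drawback is that the stated Aim 2 power becomes less favourable.

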The Beck Depression Inventory (BDI-II)⁹² is a reliable and valid self-report measure of depression.⁹³ The

Total Score of the BDI-II will be used to measure depression. This 21-item measure asks about how the subject has been feeling in the “past two weeks including today” and requires 5-10 minutes to complete.

The Five Facet Mindfulness Questionnaire (FFMQ) will be used in the study to measure mindfulness. This is a validated scale is commonly used in MBSR scientific studies. FFMQ will also provide an indication of rates of adoption of MBSR activities by participants, and permit analysis within 5 separate subscales: observing, describing, acting with awareness, nonjudging of inner experience, and nonreactivity of inner experience.⁹⁴⁻⁹⁷

We will also evaluate the feasibility and acceptability of each intervention condition. Attendance records will provide completion and retention rates. In addition, the RC will conduct a structured interview with each subject at the visit following the 8 week course to assess acceptability of the intervention.

Data Management and Statistical Analysis: We will use SPSS version 22 (IBM), and TrueCrypt 7.1a software (TrueCrypt Foundation) to enter, manage, and encrypt all electronic data. We will perform random checks and double entry of data to minimize coding errors. Data will be stored in a secured network that is backed up daily by Mount Sinai’s Information Technology Department. The distributional properties of study outcomes will be evaluated and appropriate transformations will be applied, if necessary. The equivalence of baseline characteristics of study groups will be assessed with the t-test, Wilcoxon test, or chi-square test, as appropriate. We will also assess patterns of missing data and use multiple imputation or full information maximum likelihood methods, if missing at random.

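### The Aim 2 power statement of more than 80% does not follow from its stated inputs, which give about 25% power for the RMSEA test of overall model fit

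*Combined protocol and SAP*

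**What the plan says.** The statement is in the combined protocol and SAP, section C (Approach), Data Management and Statistical Analysis, Aim 2, under Sample Size Calculations. The plan uses a published RMSEA-based method, in which the effect size is a pair of RMSEA values under the null and alternative hypotheses, "which we hypothesized would be 0.05 (adequate fit) and 0.03 (good exact fit), respectively". The other inputs are "at minimum, 80 degrees of freedom, having a sample size of 120 subjects, and an error rate (alpha) of 0.05". The conclusion is "Under these specified assumptions we will have >80% power".

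Three other places bear on the point:

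- The purpose of Aim 2 is "To explore whether changes in markers of psychosocial stress mediate the impact of MBSR on chronic inflammation".
- Aim 2 also lists descriptive fit criteria. They include an RMSEA below 0.05 and a non-significant model chi-square.
- The enrolment target comes from the Aim 1 power calculation, which asks for 100 evaluable patients and allows for attrition: "With a 120 enrolled, a 15% dropout rate provides 102 completed participants". For missing data generally, the plan will "use multiple imputation or full information maximum likelihood methods, if missing at random".

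**The concern.** Every input to the Aim 2 power figure is printed, so the figure can be checked without outside assumptions. An RMSEA of 0.05 and one of 0.03 are close together, and 120 is a small sample for separating them at 80 degrees of freedom. Power above 80% therefore looked too high.

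If the figure is wrong, the plan presents its structural equation model as adequately powered when, by the method it names, it is not. There is a second risk of misreading. This is the only power figure under Aim 2, and the aim is about mediation. A reader could take it as the chance of detecting the indirect effect through psychosocial stress, which it does not measure.

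**Working it through.** **Inputs, all from Aim 2, Sample Size Calculations:** null RMSEA ε0 = 0.05; alternative RMSEA εA = 0.03; df = 80 (a stated minimum); N = 120; alpha = 0.05. For the sensitivity case, N = 102 comes from the Aim 1 Power Calculation.

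**Method.** The model chi-square is referred to a non-central chi-square distribution with non-centrality λ = (N − 1) × df × ε². The alternative lies below the null, so the test rejects in the lower tail. This is strictly the test of not-close fit.

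**Attempt to reproduce the plan's figure (N = 120):**

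1. λ0 = 119 × 80 × 0.0025 = 23.8
2. λA = 119 × 80 × 0.0009 = 8.568
3. Critical value: lower 5% point of the non-central chi-square (80, 23.8) = 78.94
4. Power = P[non-central chi-square (80, 8.568) < 78.94] = **25.3%** (simulation with 5,000,000 draws: 25.3%)

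The stated figure is not reproduced.

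**Completers only (N = 102):** λ0 = 101 × 80 × 0.0025 = 20.2; λA = 101 × 80 × 0.0009 = 7.272; critical value 76.07; power **21.2%**.

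**Other readings at N = 120 and df = 80:**

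| Reading | Power |
|---|---|
| N in place of N − 1 | 25.6% |
| Two-sided test | 16.2% |
| Alpha 0.10 | 38.6% |
| Null and alternative swapped (upper tail, close fit) | 27.8% |
| Non-centrality doubled, as a two-group scaling | 55.1% |
| Null 0.05, alternative 0 (perfect fit) | 48.7% |

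The last row matters most. At the stated null, N, df and alpha, no alternative below 0.05 can reach 80%.

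**More degrees of freedom, stated RMSEA pair, N = 120:**

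| df | 80 | 120 | 200 | 300 | 400 | 482 |
|---|---|---|---|---|---|---|
| Power | 25.3% | 33.3% | 47.5% | 62.1% | 73.2% | 80% |

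**What 80% power would need at the stated RMSEA pair:**

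- At df = 80 and alpha 0.05, N = 367.2, so 368 subjects.
- At N = 120 and alpha 0.05, df = 481.05, so 482.
- At N = 120 and df = 80, alpha of about 0.43.

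**A pair that would exceed 80%.** Null 0.08 against alternative 0.03 gives 92.6% at N = 120 and 85.3% at N = 102. That is not the pair the plan states.

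**The descriptive cut-off is a different quantity.** At N = 120, a point estimate of RMSEA below 0.05 occurs when the chi-square is below 80 + 23.8 = 103.8. This has probability 86.2% if the true RMSEA is 0.03, and 52.0% if it is 0.05. A rule that passes about half the time at the null value is not a test at alpha 0.05, so the 86% cannot stand as the plan's power.

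**The case against.** The arithmetic is not in dispute. The case on the other side is about scope and weight.

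- **Degrees of freedom are a minimum.** The figure showing the model is not in the text available, so the actual df cannot be checked, and a larger model would have more power. This stands as a caveat. However, the plan makes its claim under the stated assumptions, so the claim has to hold at 80. Closing the gap would take about six times that number (482/80 ≈ 6.0), and the plan suggests nothing of that size.
- **The estimator differs.** The plan will use WLSMV and a latent class pattern mixture model for missingness, whereas the calculation assumes an ordinary non-central chi-square. So 25.3% is the result of the power method the plan names, not the exact operating characteristic of the planned analysis. That does not help the stated figure, which rests on the same method.
- **Power for mediation is not required.** Aim 2 is exploratory, and the plan defines its effect size openly as an RMSEA. This is fair. A clarifying clause is enough, and the missing mediation power is not the main error.
- **The completers-only figure is a lower scenario.** The planned missing-data methods may use partial data from dropouts. This also stands, and N = 120 is the main case.
- **The planned fit assessment will probably not fail.** If the true RMSEA is 0.03 at N = 120, the RMSEA cut-off is met about 86% of the time and the chi-square criterion (critical value 101.88) about 83% of the time. So 25% does not forecast failure of the descriptive criteria. That limits the consequence but does not support the power claim.

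**Conclusion.** The concern holds. On the plan's own inputs, power is about 25%, not more than 80%. No standard variant that keeps the stated RMSEA values, N, df and alpha comes near 80%: the highest tried was 55.1%. This is too large to be rounding or a software difference.

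The result assumes the usual non-central chi-square approximation with non-centrality (N − 1) × df × RMSEA², and the stated minimum of 80 df.

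The statement should be corrected, but the damage is contained. Aim 2 is exploratory, the enrolment of 120 was set by Aim 1, and the Aim 1 calculation does not use this figure.

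**What to change.** In Aim 2, Sample Size Calculations:

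1. Replace the power claim with the computed value: about 25% at N = 120, with about 21% as an optional lower scenario if only 102 completers contribute. If a different RMSEA pair or df produced the original figure, state those inputs instead and show that they reproduce it.
2. Say that the figure is power for the RMSEA test of overall model fit under the non-central chi-square approximation, and that it is not power for the indirect effect.
3. Do not describe the exploratory structural equation model as adequately powered on this basis.

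The cost is one recalculation and a few sentences. It needs no extra patients and no change to the Aim 1 sample size. The price is a less favourable stated figure.
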